1. INTRODUCTION AND BACKGROUND

In the spirit of continuous improvement, JJVC has identified a new manufacturing technology for senofilcon A. The purpose of this clinical trial is to demonstrate whether this new manufacturing technology has any clinically relevant impact on the clinical performance of the contact lens.

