14.2. Sample Size Justification

The plan is to enroll 115 subjects with a target completion of 100 subjects with approximately 50 subjects in the Test group and approximately 50 in the Control group. This is a feasibility study, and the sample size is chosen not based on estimates from historical studies with the product characteristics. The data collected for this study will be used to design future clinical trials. Thus, power calculations were conducted under different scenarios for the primary hypotheses to provide estimates on power with 2-sided type I error of 0.05 given the parallel design and 1:1 randomization ratio for average daily wear time and LogMAR visual acuity test at a 4-meter distance under high luminance/low contrast (HLLC) and low luminance/high contrast (LLHC) conditions.

Table 7 provides a summary of power based on the hypothesis of non-inferiority for logMAR visual acuity test at a 4-meter distance under either HLLC or LLHC at 1 Week Follow-up visit with a non-inferiority margin of 0.05 logMAR. Table 8 provides a summary of power based on the hypothesis of non-inferiority for average daily wear time at 1-week follow-up visit with a non-inferiority margin of 1 hour. The power calculation based on two sample t-test is conducted using the POWER procedure in SAS 9.4.

Clinical Study Protocol

Johnson & Johnson Vision Care, Inc.

Table 7: Power Calculation for the first primary hypothesis of logMAR visual acuity for either HLLC or LLHC at 2-week follow-up with a non-inferiority margin of 0.05.

Mean Difference (Test - Control)	Type I error	Standard Deviation	Total Sample Size (n/2 per arm)	Power
-0.01	0.05	0.08	100	0.981
-0.01	0.05	0.09	100	0.952
-0.01	0.05	0.10	100	0.909
0.00	0.05	0.08	100	0.928
0.00	0.05	0.09	100	0.867
0.00	0.05	0.10	100	0.799

As shown in the Table 7, the power is 0.8 or higher to show non-inferiority of the Test relative to the Control with respect to logMAR VA test at a 4-meter distance under either HLLC or LLHC when the Test - Control ≤ 0 and the standard deviation for both Test and Control < 0.10 .

Table 8: Power Calculation for the second primary hypothesis of average daily wear time at 2-week follow-up with a non-inferiority margin of 1.

Mean Difference (Test - Control)	Type I error	Standard Deviation	Total Sample Size (n/2 per arm)	Power
-0.05	0.05	1.90	100	0.799
-0.05	0.05	1.93	100	0.788
0.00	0.05	1.90	100	0.834
0.00	0.05	1.93	100	0.823
0.05	0.05	1.90	100	0.864
0.05	0.05	1.93	100	0.855

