14.3. Analysis Populations

Safety Population:

All subjects who are administered any test article excluding subjects who drop out prior to administering any test article. At least one observation should be recorded.

Per-Protocol Population:

All subjects who successfully complete all visits and do not substantially deviate from the protocol as determined by the trial cohort review committee prior to database hard lock. Justification for the exclusion of subjects with protocol deviations from the per-protocol population set will be documented in a memo to file.

Intent-to-Treat (ITT) Population:

All randomized subjects regardless of actual treatment and subsequent withdrawal from the study or deviation from the protocol. At least one observation should be recorded.

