14.5. Primary Analysis

The co-primary endpoints for this study are the logMAR VA test at a 4-meter distance under either HLLC or LLHC and the average daily wear time at 2-week follow-up evaluated after 14 ± 4 days of lens wear. The primary analysis will be conducted on per-protocol populations.

Visual Performance

Monocular distance visual performance in logMAR scale at follow-up visits will be analyzed using a mixed model of repeated measurement (MMRM) for HLLC and LLHC respectively to compare between Test and Control lenses at 2-week follow-up. The model will include baseline logMAR, lens type, visit, and the interaction of lens type and visit as the fixed effect, and investigational site and patient as random effects. Baseline demographics such as age and gender have historically limited influence on objective visual performance; thus, in accordance with the principle of parsimony, will not be included in the model. The covariance of residual errors between two follow-up visits across periods for the same eye and subject across wearing periods will be modeled using an unstructured (UN) covariance structure.

The null and alternative hypotheses for non-inferiority of Test lens relative to Control are as follows:

$$H_0: \Delta > 0.05$$
$$H_A: \Delta \leq 0.05$$

Clinical Study Protocol

Johnson & Johnson Vision Care, Inc.

where Δ is the mean difference in logMAR between Test lens and Control lens (Test minus Control) at 2-week follow-up. Non-inferiority will be declared if the upper bound of the confidence interval of the mean difference between Test and Control is less than 0.05.

Average Daily Wearing Time

Average daily wear time will be analyzed using a similar MMRM model with fixed and random effects described in the primary analysis. Age and gender will also be included as fixed effects.

The null and alternative hypotheses for non-inferiority of Test lens relative to Control are as follows:

$$H_0: \Delta < -1$$
$$H_A: \Delta \geq -1$$

where Δ is the mean difference in average daily wearing time between Test lens and Control lens (Test minus Control) at 2-week follow-up. Non-inferiority will be declared if the lower bound of the confidence interval of the mean difference between Test and Control is greater than -1.

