14.6. Secondary Analysis

CLUE Comfort and Vision scores

CLUE scores at follow-up visits will be analyzed using a MMRM model for comfort and vision respectively to compare between Test and Control lenses at 2-week follow-up. Each regression model will include the baseline score, lens type, visit, and the interaction of lens type and visit as fixed effects and investigational site as a random effect (G-side). Age and gender will also be included as fixed effects. The covariance of residual errors between different periods for the same subject will be modeled using an unstructured (UN) covariance structure. The Kenward and Roger method will be used for the calculation of the denominator degree of freedom.⁸

The null and alternative hypotheses for non-inferiority of Test lens relative to Control are as follows:

$$H_0: \Delta < -5$$
$$H_A: \Delta \geq -5$$

where Δ is the CLUE score mean difference between Test lens and Control lens (Test minus Control) at 2-week follow-up. The hypothesis will be tested via the corresponding two-sided 95% confidence interval (CI) for least squares mean (LSM) difference (Test - Control) in CLUE scores. Non-inferiority will be declared if the lower bound of the confidence interval of the mean difference between Test and Control is greater than -5.

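### Both co-primary non-inferiority tests use only per-protocol completers and no analysis is assigned to ITT by name, so an excess of lens failures on Test would move the result towards non-inferiority

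*Combined protocol and SAP*

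**What the plan says.** Section 14.5: "The primary analysis will be conducted on per-protocol populations". This covers both co-primary endpoints, logMAR acuity (margin 0.05) and average daily wear time (margin 1 hour). Section 2.3 makes study success depend on meeting both.

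Section 14.3 defines the per-protocol set as "All subjects who successfully complete all visits and do not substantially deviate from the protocol". A cohort review committee makes that judgement before the database is locked. The same section defines ITT as "All randomized subjects regardless of actual treatment and subsequent withdrawal from the study or deviation from the protocol", with at least one observation. Sections 14.5 to 14.9 do not mention ITT: 14.6 names no population, and 14.7 and 14.8 are marked not applicable.

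In section 7.2 the lens is assigned at step 1.16. A subject can be removed after that for:

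- unacceptable fit (steps 1.24, 2.8, 3.9);
- acuity worse than 20/30 in either eye (steps 1.27, 2.16);
- unsuccessful dispensing because of vision, comfort or fit, or failure to keep the wear schedule (section 8.2).

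Section 14.9 imputes nothing and relies on the mixed model under missing-at-random. It promises further, unspecified sensitivity analyses only if more than 15% of data are missing. Section 2.2 has reasons for discontinuation and fit acceptability summarised descriptively.

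**The concern.** The reasons for removal overlap with what the co-primaries measure. A subject who sees poorly through the lens, or cannot wear it for long, is the kind of subject who leaves and so falls outside the analysed set. If the new process produces more such subjects, or worse ones, the remaining completers look more alike than the randomised groups are.

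The mixed model does not repair this. At Visit 2, wear time (step 2.2) and ETDRS acuity (step 2.7) are recorded before the fit and continuance decisions (steps 2.8 and 2.16). These are the data a missing-at-random model would use, but the per-protocol set has already dropped those subjects.

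An imbalance would be visible in the descriptive tables but would not enter the success rule. The stake is the answer to the study's own question, "whether this new manufacturing technology has any clinically relevant impact on the clinical performance of the contact lens", and what is carried forward, since "The data collected for this study will be used to design future clinical trials".

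**Working it through.** **Inputs from the documents.** Margins of 0.05 logMAR and 1 h (2.3); SDs of 0.08–0.10 logMAR and 1.90–1.93 h (Tables 7 and 8); 50 completers per arm; 115 enrolled and 100 completing (14.2).

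**Assumptions.** Failure fractions and the outcome in failures are not given. I take each failure as *d* = 4 h or 0.2 logMAR worse than the completers of its own arm, and vary the Test excess. Section 14.5 gives no confidence level ("Non-inferiority will be declared if the lower bound of the confidence interval of the mean difference between Test and Control is greater than -1"). Each result is therefore shown as two-sided 95% interval / one-sided 0.05.

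**Step 1: the plan's own figures.** The standard error is SD × √(2/50) = 0.2 × SD. Power is the upper tail of a noncentral t on 98 df with noncentrality (distance to margin)/SE. For wear time with difference 0 and SD 1.90, SE = 0.38 and the noncentrality is 1/0.38 = 2.63. Power is 0.834 at one-sided 0.05, as in Table 8, and 0.741 at one-sided 0.025. One-sided 0.05 reproduces all 12 rows of Tables 7 and 8; one-sided 0.025 reproduces none.

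**Step 2: size of the shift.** An arm's all-randomised mean is its completer mean made worse by *p·d*, where *p* is its failure fraction. Hence

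all-randomised deficit = completer deficit + (p_Test − p_Control) × d.

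Equal fractions and equal severity give zero shift. With the all-randomised deficit at the margin, the completer deficit lies (p_Test − p_Control) × d inside it.

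**Step 3: chance that one endpoint falsely passes.** Example: a 10-point excess on wear time hides 0.10 × 4 = 0.4 h. The noncentrality is 0.4/0.38 = 1.05 and the probability is 0.179 / 0.274.

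| Test excess | Hidden difference | Wear time | logMAR |
|---|---|---|---|
| 0 points | 0 | 0.025 / 0.05 | 0.025 / 0.05 |
| 1 point | 0.04 h; 0.002 | 0.032 / 0.062 | 0.031–0.033 / 0.061–0.064 |
| 2 points | 0.08 h; 0.004 | 0.040 / 0.075–0.076 | 0.039–0.043 / 0.074–0.081 |
| 5 points | 0.2 h; 0.01 | 0.074–0.075 / 0.129–0.131 | 0.071–0.090 / 0.125–0.153 |
| 10 points | 0.4 h; 0.02 | 0.175–0.179 / 0.269–0.274 | 0.166–0.235 / 0.257–0.343 |

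Severity alone can do the same. With 7.5 of 57.5 failing in each arm but Test failures worse by an extra 2 h, the shift is 7.5/57.5 × 2 = 0.26 h and the probability 0.10 / 0.17 (SD 1.90).

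**Step 4: both endpoints.** Success needs both. If Test is at the margin on both, the endpoints are independent and the excess is 10 points, joint false success is 0.175 × 0.166 = 0.029 to 0.179 × 0.235 = 0.042 (two-sided 95%), or 0.269 × 0.257 = 0.069 to 0.274 × 0.343 = 0.094 (one-sided 0.05). The single-endpoint rates carry over to study success only if the other endpoint is comfortably non-inferior.

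**Step 5: the 15% clause.** Planned loss is 15/115 = 13.0%. The clause needs more than 0.15 × 115 = 17.25, so 18 or more. A 10-point Test excess is about 6 subjects (0.10 × 57.5). Inside the planned 15 it does not trigger the clause. On top of them, (15 + 6)/115 = 18.3% does, if missingness is counted on all randomised subjects. Sections 5.3 and 8.2 provide for replacing discontinued subjects, so 115 is itself an assumption.

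**Step 6: what ITT recovers.** Simulation for wear time: 57 per arm, SD 1.9, 10% failures on Test and none on Control, d = 4 h, baseline and site omitted. The per-protocol test falsely passes in about 18–20% / 28–30%. If failures leave at Visit 2, the ITT mixed model brings this to about 8%, 5%, 3% / 14%, 10%, 6% at visit correlations of 0.5, 0.7, 0.9. If they leave at Visit 1 there is no follow-up value and no gain (18–19% / 28–30%).

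**The case against.** **Feasibility study.** Section 2.3 calls all hypotheses exploratory, and section 14.2 says the sample size does not rest on historical estimates. This lowers the consequence. It does not remove the point, because a success rule is stated and the data feed later trials.

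**Per-protocol is a usual choice for non-inferiority.** It guards against deviations that dilute a real difference, so it is a reasonable primary here. It does not guard against exclusions that are themselves lens failures.

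**A large excess is unlikely.** Table 1 gives both lenses the same material, base curve, diameter and powers, and a deficit of 4 h or 0.2 logMAR is 2 or more SDs. This stands: the 10-point row is an upper illustration, and at 1–2 points the rates are near nominal.

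**The target is a choice.** A subject stopped at the Visit 1 fitting never has a study wear time, so giving one a value defines a composite. That is fair, and is why the range should be the sponsor's and stated beforehand.

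**Stronger readings the documents do not support.**

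- A reader might infer that the analysis is biased towards non-inferiority as it stands. No failure rate by arm is given, so the direction is conditional.
- A reader might infer a 17–24% or 26–34% chance of false study success. Those rates are per endpoint (step 4).
- A reader might infer that the 15% clause can never act (step 5 shows that it can).
- A reader might infer that every failure leaves the set automatically. A subject who fails on fit at Visit 3 has attended every visit: 14.3 does not address the case, though 8.1 does not count a withdrawn subject as completed. A low-wear subject who attends all visits is excluded only if the cohort review committee finds a substantial deviation.

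**Conclusion.** The point holds in conditional form. Both co-primary tests rest on completers alone, no analysis is assigned to ITT by name, and the removal grounds are tied to the endpoints. If failures are more frequent or worse on Test, the per-protocol difference is too favourable; if they are equal in number and severity, it is not.

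Per endpoint, under the assumed deficits and with the all-randomised difference at the margin, false non-inferiority is 3–4% / 6–8% at a 1–2 point excess, 7–9% / 13–15% at 5 points and 17–24% / 26–34% at 10 points, against 2.5% / 5%. If Test is at the margin on both independent endpoints, joint false success at 10 points is about 3–4% / 7–9%. These figures are illustrations, not estimates for this study. The gap should be fixed because the repair is cheap. It is not a reason to abandon the per-protocol primary.

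**What to change.** Keep the per-protocol primary and leave the clinical withdrawal rules unchanged. Then:

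1. In 14.5, pre-specify the same mixed models on the ITT population as a supportive analysis, using all recorded Visit 2 and Visit 3 data from withdrawn subjects. Report it beside the per-protocol result and discuss any disagreement.
2. Add one sensitivity analysis, run whether or not the 15% clause is met, that gives lens-related failures an unfavourable value over a pre-stated range chosen by the sponsor. Report the severity at which the conclusion changes. This is needed because ITT alone recovers nothing for Visit 1 exits.
3. Report lens-related discontinuation by arm and reason on all randomised subjects.
4. In 14.9, compute the percentage of missing data on all randomised subjects.

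The cost is SAP wording, a second run of the same models and one sensitivity analysis on data already collected, with the possibility of a less favourable supportive result. As a supportive analysis it costs no power. Making success depend on both populations would cost power and is not proposed here. The unstated confidence level in 14.5 is a separate point.

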2.3. Hypotheses

This is a feasibility study and all the hypotheses are exploratory in nature.

Primary Hypotheses:

There are two co-primary hypotheses in this study. Both of them must be met to satisfy the primary objective of the study.

1. The Test lens will be non-inferior to the Control lens with respect to logMAR visual performance (using ETDRS visual acuity charts) at the 2-week follow-up visit. A non-inferiority margin of 0.05 logMAR will be used.
2. The Test lens will be non-inferior to the Control lens with respect to average daily wear time at 2-week follow-up visit. A non-inferiority margin of 1 hour will be used.

Secondary Hypotheses:

1. The Test lens will be non-inferior to the Control lens with respect to overall CLUE comfort score at the follow-up visit. A non-inferiority margin of -5 points will be used.
2. The Test lens will be non-inferior to the Control lens with respect to overall CLUE vision score at the follow-up visit. A non-inferiority margin of -5 points will be used.

All primary hypotheses of this study have to be met for study success.

Clinical Study Protocol

Johnson & Johnson Vision Care, Inc.

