7.2. Detailed Study Procedures

VISIT 1

The subjects must present to Visit 1 wearing their habitual contact lenses.

Visit 1: Screening		
Step	Procedure	Details
1.1	Statement of Informed Consent	
Each subject must read, understand, and sign the Statement of Informed Consent before being enrolled into the study. The Principal Investigator or his/her designee conducting the informed consent discussion must also sign the consent form.
 
Note: The subject must be provided a signed copy of this document.

1.2	Demographics	Record the subject's year of birth, age, gender, race and ethnicity.
1.3	Medical History and Concomitant Medications	Record the subject's medical history and concomitant medications.
1.4	Habitual Lenses	Record the subject's habitual lens type, parameters, wear modality and duration.
1.5	Contact lens wear times	Record the current wear time (WT) and comfortable wear time (CWT).
1.6	Eligibility after Screening	
All responses to Screening Inclusion Criteria questions must be answered "yes" and all responses to Exclusion Criteria must be answered "no" for the subject to be considered eligible.
 
If subject is deemed to be ineligible after screening, proceed to Final Evaluation and complete Subject Disposition. Refraction and Biomicroscopy forms do not need to be completed as part of Final Evaluation.

Visit 1: Baseline		
Step	Procedure	Details
1.7	Background PRO Questionnaire	Subject will complete questions regarding their experiences with their habitual lenses.
1.8	Subject-reported Ocular Symptoms	Subject Reported Ocular Symptoms and Problems

Clinical Study Protocol
Johnson & Johnson Vision Care, Inc.

Visit 1: Baseline		
Step	Procedure	Details
1.9	Distance visual acuity (VA)	Record the distance Snellen VA for OD, OS and OU with their habitual contact lenses in place. Subject must keep reading smaller lines until less than half the letters are correctly identified.
1.10	Remove habitual lenses	The subject's habitual lenses will be removed and stored in their own lens case. If they forgot to bring their lens case, one will be provided to them.
1.11	Subjective spherocylinder refraction and VA	Perform binocular subjective best spherocylinder refraction and record the best corrected Snellen VA for OD, OS and OU.

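### Free improvement: Section 14.5 should write out the co-primary wear-time model and name the habitual wear time recorded at Visit 1 as its baseline covariate, in place of baseline logMAR

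*Combined protocol and SAP*

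**What the plan says.** Section 14.5 sets out the visual-acuity model first: "The model will include baseline logMAR, lens type, visit, and the interaction of lens type and visit as the fixed effect". Site and patient are random effects, and the residual covariance between follow-up visits is defined for the same eye and subject. For the second co-primary endpoint it then says: "Average daily wear time will be analyzed using a similar MMRM model with fixed and random effects described in the primary analysis". The one stated change is: "Age and gender will also be included as fixed effects". No baseline value of wear time is named there or elsewhere in Section 14.

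That baseline is collected. Section 7.2, Visit 1 screening, step 1.5, tells the site: "Record the current wear time (WT) and comfortable wear time (CWT"). Table 3 also marks contact lens wear time at Visit 1. Section 5.1 requires baseline information to be in hand before randomization.

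The secondary models in Section 14.6 are explicit on the same point: "Each regression model will include the baseline score, lens type, visit, and the interaction of lens type and visit as fixed effects". Each CLUE outcome is adjusted for its own baseline.

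On wear time, Section 2.3 says: "A non-inferiority margin of 1 hour will be used". Both co-primary hypotheses must be met for study success.

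**The concern.** Taken at its word, the cross-reference gives the wear-time model a covariate with three problems.

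- Nothing in the documents links acuity to hours of wear.
- It is an eye-level quantity, with two values per subject, while wear time has one.
- Its source is undefined. Table 3 schedules ETDRS logMAR acuity only at Visits 2 and 3, and Visit 1 acuity is Snellen.

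Meanwhile the pre-randomization value of the outcome itself is left out. If habitual and study wear time are correlated, leaving it out makes the confidence interval wider than it need be, on a test that must succeed. Chance differences between arms in habitual hours also go unadjusted. A second cost is that, if the cross-reference is ambiguous, the main covariate of a co-primary test is left to be settled by the analyst after the fact.

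**Working it through.** **1. The plan's own figure.** Inputs are the margin of 1 hour (Section 2.3), and SD 1.93, true difference 0, total N 100 and printed power 0.823 (Table 8, Section 14.2). The method is a two-sample t-test with no covariate.

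- Standard error = SD × √(2/n) = 1.93 × √(2/50) = 1.93 × 0.2 = 0.386 h.
- Noncentrality = (margin + true difference)/SE = 1/0.386 = 2.591, with df = 98.
- Noncentral-t power at **one-sided 0.05**: 0.823, which matches Table 8. With SD 1.90 the result is 0.834, also as printed. All 12 rows of Tables 7 and 8 reproduce at this level.
- At one-sided 0.025 (a two-sided 95% interval) the same case gives 0.727, and no row of either table reproduces.

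The level matters because Section 14.2 describes "power with 2-sided type I error of 0.05 given the parallel design and 1:1 randomization ratio", while Section 14.5 states no confidence level for the primary intervals. Both levels are therefore shown below.

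**2. With Visit 1 wear time as covariate.** Let ρ be the correlation between Visit 1 and Week 2 wear time. The documents do not give it, so it is assumed over a range.

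- Residual SD = 1.93 × √(1 − ρ²).
- SE = residual SD × 0.2, noncentrality = 1/SE, and df = 97 (one more parameter).
- Equivalent unadjusted N = 100/(1 − ρ²).

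| Assumed ρ | Residual SD (h) | Noncentrality | Power, one-sided 0.05 | Power, two-sided 95% CI | Equivalent N |
|---|---|---|---|---|---|
| no covariate | 1.930 | 2.591 | 0.823 | 0.727 | 100 |
| 0.1 | 1.920 | 2.604 | 0.827 | 0.732 | 101 |
| 0.3 | 1.841 | 2.716 | 0.854 | 0.767 | 110 |
| 0.5 | 1.671 | 2.991 | 0.908 | 0.842 | 133 |
| 0.7 | 1.378 | 3.628 | 0.975 | 0.949 | 196 |

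The gain at one-sided 0.05 runs from 0.827 − 0.823 = 0.004 (negligible) to 0.975 − 0.823 = 0.152. With a two-sided 95% interval it runs from 0.732 − 0.727 = 0.005 to 0.949 − 0.727 = 0.222. The calculation treats Week 2 as a single comparison and ignores any contribution from age, gender, site and the Week 1 visit, as Table 8 does.

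**3. Structure of the inherited model.** An eye-level residual covariance cannot be applied to one value per subject per visit. With two follow-up visits, an unstructured within-subject covariance already has its full three parameters (two variances and one covariance), so a patient random intercept on top of it could not be separately estimated. The Section 14.6 layout, with site random and an unstructured covariance within subject, fits wear time directly.

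**The case against.** The best reply is that Section 14.5 says similar, not identical. The eye-level terms cannot carry over to wear time, so some adaptation is implied. Section 14.6 shows the sponsor's practice of using each outcome's own baseline, and the wear-time baseline is scheduled. On that reading the sponsor already intends the right model. This stands as far as intent goes: the text is ambiguous and does not prove a choice of baseline logMAR. It does not remove the need for the change. The sentence refers to effects already described, lists the one addition and names no wear-time baseline. Section 14.10 commits to analysis as specified in those sections.

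It is also fair to say that ρ is unknown and may be low. Section 3.2 requires at least 6 hours of habitual wear per day, and the study asks for the same minimum, which may narrow the range. That the study is a feasibility study with hypotheses labelled exploratory also limits what is at stake.

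Three stronger readings are tempting, and the documents do not support them.

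- **That the study is underpowered because of the omission.** Table 8 assumes no covariate, so its figures do not depend on one. Randomization also keeps the unadjusted estimate unbiased.
- **That wear time is the lower-powered of the two co-primary tests.** At true difference 0, logMAR power is 0.928, 0.867 and 0.799 for SD 0.08, 0.09 and 0.10, against 0.834 and 0.823 for wear time. The ordering reverses at logMAR SD 0.10.
- **That the covariate would adjust for imbalance between reusable and daily disposable wearers.** It would do so only as far as modality acts through hours worn, since the model has no modality term.

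**Conclusion.** The point holds as a free improvement. Section 14.5 leaves the baseline covariate of a co-primary model to a cross-reference. Read literally, that reference selects a value that is not scheduled on the logMAR scale at Visit 1 and is at the wrong level, and it omits the relevant value already in the database. The benefit of correcting it is precision plus an unambiguous pre-specification.

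The size of the benefit rests entirely on the assumed correlation: negligible at 0.1, modest at 0.3, and worth about a third more subjects at 0.5 (133 against 100). It matters more if the interval is two-sided 95%. There, SD 1.93 gives 0.727 without the covariate, and of the correlations shown only 0.5 and 0.7 bring power above 0.80. The assumptions are true difference 0, 50 completers per arm, a linear relation between habitual and study wear time, and a Visit 1 value measured in much the same way as the endpoint.

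**What to change.** In Section 14.5, replace the cross-reference with an explicit wear-time model:

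- **Fixed effects:** Visit 1 habitual average daily wear time, lens type, visit, lens type × visit, age and gender.
- **Random effect:** investigational site.
- **Residual covariance:** unstructured across the two follow-up visits within subject, not within eye.
- **Removed:** baseline logMAR.

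Add a sentence defining the covariate. Section 2.2 defines the endpoint as hours from reported insertion to removal on an average day, while step 1.5 gives no calculation rule. The baseline should be derived in the same way as far as the step 1.5 data allow, and any difference should be stated. While editing, state the confidence level of the primary intervals, since the value of the covariate depends on it.

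The cost is two or three sentences in Section 14.5. No visit, assessment or sample-size change is needed. It should be settled before the mask is broken.
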